### 8.3. Immunogenicity analysis

### 8.3.1. Primary end-point analysis

For each vaccination schedule, GMTs of the hSBA titres to the three analysed 4CMenB antigens (fHbp, NadA and PorA) will be calculated with 95% confidence intervals. Schedules will be compared using unpaired t-tests on log-transformed titres or the Kruskal Wallis test if log-titres are not normally distributed. Proportions with titres ≥1:4 will also be calculated with exact binomial 95% confidence intervals and compared between groups by Fisher's exact test. Significance will be at a 5% level with no adjustment for multiple comparisons since whilst there are three antigens there are only two groups being compared.

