## 2. Trial Design Summary

This is a multicentre, open label, phase IV study at several participating NHS sites in England. Term, healthy infants (born at  $\geq$ 37 weeks gestation), aged  $\geq$ 56 days to  $\leq$  70 days are randomised to one of two 4CMen B schedules:

- Group 1: 4CMenB Bexsero® at 2, 3 and 12 months of age; PCV13 at 4 months of age
- Group 2: 4CMenB Bexsero® at 2, 4 and 12 months of age; PCV13 at 3 months of age

All other routine immunisations are received alongside the above allocation, as per the UK vaccination schedule. Infants remain in the study from recruitment to around 13 months of age with blood sample schedule as below. After each vaccination visit, parents/caregivers complete a 7 day paper diary for collection of solicited AEs (temperature, redness, swelling, tenderness, feeding, activity, irritability, persistent crying, diarrhoea, vomiting). All other unsolicited AEs are collected at each visit by study staff. SAEs and AESIs are collected from the time of consent to last visit. AESIs for this study were: Febrile seizures, arthritis.

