### 2.2. Randomisation and blinding

Participants are randomised in a 1:1 ratio between groups 1 and 2. A computerised block randomisation list is produced for each site, placed inside an opaque envelope with corresponding participant number. At recruitment, each participant is allocated, in order of inclusion, the next available participant number from the randomisation. Prior to first vaccinations, the local study team will open the envelope and reveal the group number allocation and so vaccination schedule to be followed.

This is an unblinded study; both study teams and participants are aware of their allocation. However, laboratory staff testing the vaccine responses will be blinded to group allocation.

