#### 8.3.3 Exploratory analysis

Multivariable normal errors regression models on logged titres will be used to adjust for interval to blood from vaccination and other demographic factors (e.g. gestation, age at first vaccination, sex) to assess whether any differences between groups are explained by these factors.

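### Randomisation is blocked within site but the primary and secondary comparisons have no site term: a valid, conservative test that gives up a modest amount of precision

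*SAP*

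**What the plan says.** SAP section 2 describes a "multicentre, open label, phase IV study at several participating NHS sites in England". Section 2.2 sets the allocation: "Participants are randomised in a 1:1 ratio between groups 1 and 2", and "A computerised block randomisation list is produced for each site". Randomisation is therefore stratified by site. The SAP gives neither the number of sites nor the block size.

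Section 8.3.1 fixes the primary analysis: "Schedules will be compared using unpaired t-tests on log-transformed titres", with the Kruskal-Wallis test as the fallback for non-normal log titres. Proportions with titres of 1:4 or above are "compared between groups by Fisher's exact test". No site or covariate term appears. The section asks for GMTs with intervals per schedule but does not name a between-schedule geometric mean ratio. Section 8.3.2 carries the same methods to the secondary endpoints and adds fold change between time points.

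Section 8.3.3 keeps regression on logged titres as exploratory. Its purpose is to see whether factors account for a difference, and it would "adjust for interval to blood from vaccination and other demographic factors (e.g. gestation, age at first vaccination, sex" among others. Site is not named. The recruiting site appears only as a baseline descriptor in section 8.2.

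**The concern.** Blocking within site balances the arms on site. Between-site variation then largely drops out of the true variability of the difference between arms, but an unpaired t-test still counts it as noise. If sites differ in titre, the reported standard error is larger than the true one, intervals over-cover and some power is lost. Including the stratification factor recovers this and brings the analysis into line with the design.

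Gestation, age at first vaccination and sex raise a different and weaker issue. They are not stratification factors. The unadjusted standard error already allows correctly for chance imbalance in them, so adjusting for them is an optional gain in precision and corrects no error.

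What is at stake is precision in a trial sized at 80% power for its target difference.

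**Working it through.** **Inputs from the SAP.** SD 1.0 log_e units, 1.49-fold difference, 80% power, 5% significance, 10% drop-out, 110 per group (section 3); two-sided intervals (section 6.3). Section 3 also mentions 60 per arm. That is a separate inconsistency; the 110 figure is the one tied to the 1.49-fold difference.

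**Assumed, because the SAP gives no figure.** Site ICC 0 to 0.20; share of variance explained by site plus baseline covariates (R²) 0 to 15%; 4 or 8 equal sites; blocks of 4.

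**Step 1: reproduce the plan.** ln(1.49) = 0.3988. n per arm = 2 × (1.960 + 0.842)² × 1.0² / 0.3988² ≈ 98.7, so 99. With drop-out, 99 / 0.90 = 110 per group, 220 in total. The stated target reproduces. It rests on the total SD, so it already assumes an unadjusted comparison. Power at 99 per arm is 80.1% by the normal approximation and 79.7% by the noncentral t.

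**Step 2: effect of site alone.** Blocked randomisation within site was simulated with 198 infants, total variance 1.0 and 6,000 runs per cell. The unpaired t-test was compared with a model containing site.

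| Sites | ICC | Type I error, unadjusted | Power, unadjusted | Power, with site | Gain (points) |
|---|---|---|---|---|---|
| 4 | 0 | 0.044 | 79.5% | 79.5% | 0 |
| 4 | 0.02 | 0.045 | 80.5% | 80.7% | 0.2 |
| 4 | 0.05 | 0.044 | 81.0% | 81.9% | 0.9 |
| 4 | 0.10 | 0.035 | 82.1% | 84.1% | 2.0 |
| 4 | 0.20 | 0.036 | 83.6% | 87.5% | 3.9 |
| 8 | 0 | 0.052 | 80.9% | 80.6% | -0.3 |
| 8 | 0.02 | 0.047 | 80.0% | 80.4% | 0.4 |
| 8 | 0.05 | 0.046 | 80.4% | 81.7% | 1.3 |
| 8 | 0.10 | 0.044 | 81.2% | 83.6% | 2.4 |
| 8 | 0.20 | 0.033 | 82.7% | 88.1% | 5.4 |

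The Monte Carlo standard error of a 5% rejection rate is √(0.05 × 0.95 / 6,000) ≈ 0.003, so the two ICC 0 rows are compatible with 0.05. Coverage of the unadjusted 95% interval is about 95% to 97%. The error runs one way: intervals too wide, test conservative.

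**Step 3: site and baseline covariates together.** The residual SD becomes √(1 − R²) and the effective sample size 99 / (1 − R²). Power is from the noncentral t at a standardised difference of 0.3988 / √(1 − R²) with 99 per arm.

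| Assumed R² | Effective n per arm | Power | Detectable ratio at 80% power |
|---|---|---|---|
| 0 | 99 | 79.7% | 1.49 |
| 5% | 104 | 81.7% | 1.477 |
| 10% | 110 | 83.7% | 1.462 |
| 15% | 116 | 85.7% | 1.446 |

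**Step 4: cost of adjusting.** With 198 infants the t-test has 198 − 2 = 196 degrees of freedom. With 8 sites and three covariates the model has 198 − 8 − 1 − 3 = 186. The loss is negligible.

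**The case against.** The strongest reply is that the planned test is valid and agrees with the sample size. The 110 per group was derived for an unadjusted comparison at a total SD of 1.0, so adjustment would be a bonus and repairs no shortfall. That stands. So does the point that the size of the gain is entirely assumed and is zero if site has no bearing on titre.

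A reader might infer that ignoring the strata makes the error bars wrong in a way that threatens the conclusions. The documents do not support this. The fault can only widen the intervals, and it applies to site alone.

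A reader might also take gestation, age at first vaccination and sex to be known predictors of titre left out of the primary model. Section 8.3.3 offers them only as examples of factors that might explain a difference, and the SAP gives no evidence that they predict titre. Eligibility in section 2 also limits what they can explain: infants are term, and entry age spans 56 to 70 days, a range of 14 days.

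Finally, the covariate list in section 8.3.3 is illustrative and regression is already planned, so site could still enter. But it would do so only in an exploratory model, with the choice left open in an unblinded trial. None of these replies explains why the primary comparison should omit the factor by which the trial randomises.

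**Conclusion.** The point holds as a modest matter of matching analysis to design. The primary and secondary comparisons omit the stratification factor. If site is related to titre, they are conservative and give up some precision. Neither the validity of the test nor the planned 80% power is in question.

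Under assumed site ICCs up to 0.10 the recoverable power is about 0 to 2.5 points, and at 0.20 about 4 to 5 points. If site and covariates together explain at most 15% of variance, power reaches at most about 86% and the detectable ratio falls from 1.49 to no lower than about 1.45. These figures rest on the assumed ICC, R², number of sites and block size; only the 79.7% starting point follows from the SAP's own inputs. The change is worth making because it is nearly free, not because the planned analysis fails.

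**What to change.** In section 8.3.1, make the primary GMT comparison a linear regression of log titre on schedule group and site (fixed effect), with age at first vaccination, gestation and sex as pre-specified baseline covariates. Report the adjusted geometric mean ratio with its 95% interval.

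- Set the rule for pooling small sites before data release. Section 1.3 already requires the plan to be final by then.
- Leave interval to blood out of the primary model. It is determined after randomisation and can stay in the exploratory model of section 8.3.3.
- For titres of 1:4 or above, use a site-stratified (Mantel-Haenszel) risk difference. Keep Fisher's exact test where strata are sparse, by a criterion stated in advance.
- Keep the unadjusted t-test or rank test as a sensitivity analysis, and say that this covers the case of non-normal log titres.
- Apply the same approach to the secondary endpoints through section 8.3.2.

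The cost is SAP wording and a few degrees of freedom. No new data are needed: site and the three covariates are already listed for the baseline summary in section 8.2.

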### 8.3.2. Secondary end-point analysis

This will be done in the same way as the primary end-point analysis described in 8.3.1. In addition, the geometric mean fold change between time points will be calculated with 95% confidence intervals.

#### 8.3.3 Exploratory analysis

Multivariable normal errors regression models on logged titres will be used to adjust for interval to blood from vaccination and other demographic factors (e.g. gestation, age at first vaccination, sex) to assess whether any differences between groups are explained by these factors.

# 8.4. Safety analysis

Descriptive summary in table form of solicited AEs at each visit for the two vaccination schedules will be reported along with proportions and numbers of Grade 3 AEs. SAEs and AESIs will be summarised and proportion in each schedule group reported. MAAEs frequency and disease category will be reported by vaccine schedule group across the whole duration of the study.

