### 4.3. Safety objectives

- 1. To describe the safety of 4CMenB when given concomitantly with routine vaccines at 2 and 3 months of age (Group 1).
- 2. To describe the safety of 4CMenB when given concomitantly with routine vaccines at 2 and 4 months of age (Group 2).
- 3. To describe the safety of PCV13 when given concomitantly with routine vaccines at 3 months of age (Group 2).
- 4. To describe the safety of PCV13 when given concomitantly with routine vaccines at 4 months of age (Group 1).
- 5. To describe the safety of 4CMenB booster when given concomitantly with routine vaccines at 12 months of age (Group 1 and 2).
- 6. To describe the safety of PCV13 booster when given concomitantly with routine vaccines at 12 months of age (Group 1 and 2).

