# 5.3. Observational end points: Safety data

Objective	Outcome Measures
-----------	------------------

To describe the safety of 4CMenB when given concomitantly with routine vaccines at 2 and 3 months of age (Group 1).

To describe the safety of 4CMenB when given concomitantly with routine vaccines at 2 and 4 months of age (Group 2).

To describe the safety of PCV13 when given concomitantly with routine vaccines at 3 months of age (Group 2).

To describe the safety of PCV13 when given concomitantly with routine vaccines at 4 months of age (Group 1).

To describe the safety of 4CMenB booster when given concomitantly with routine vaccines at 12 months of age (Group 1 and 2).

To describe the safety of PCV13 booster when given concomitantly with routine vaccines at 12 months of age (Group 1 and 2).

- 1. Occurrence, nature, time of onset, duration, intensity, action taken and whether the event led to early termination from the study, of any solicited AEs within 7 days after each vaccination(s).
- 2. Occurrence, nature, time of onset, duration, intensity, action taken and whether the event led to early termination from the study, of any unsolicited AEs within 28 days after each vaccination(s).
- 3. Occurrence, nature, time of onset, duration, intensity, action taken and whether the event led to early termination from the study, of any medically attended AEs for the whole duration of the study.
- 4. Occurrence, nature, time of onset, duration, intensity, action taken, relationship to vaccination, outcome and whether the event led to early termination from the study, of any SAEs and AESIs for the whole duration of the study.

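### Medically attended adverse events are reported only as a whole-study total per schedule, and no breakdown by dose or time since vaccination is specified for SAEs and AESIs

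*SAP*

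**What the plan says.** SAP section 8.4 treats the safety event classes differently.

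- **Solicited AEs** are broken down by visit: "Descriptive summary in table form of solicited AEs at each visit for the two vaccination schedules will be reported", together with numbers and proportions of Grade 3 events.
- **SAEs and AESIs** have no stated period, visit or dose: "SAEs and AESIs will be summarised and proportion in each schedule group reported".
- **MAAEs** are pooled explicitly: "MAAEs frequency and disease category will be reported by vaccine schedule group across the whole duration of the study".

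The safety objectives in section 4.3 are tied to vaccine and age. Objective 1, for example, concerns 4CMenB in Group 1 at 2 and 3 months. Objective 2 is its Group 2 counterpart at 2 and 4 months. Objectives 3 and 4 concern PCV13 at 3 months (Group 2) and at 4 months (Group 1). Objectives 5 and 6 concern the two boosters at 12 months in both groups.

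Section 5.3 sets the MAAE outcome as occurrence, onset time and other features "of any medically attended AEs for the whole duration of the study". The SAE and AESI outcome has the same period and adds relationship to vaccination. Section 2 gives the collection period: "SAEs and AESIs are collected from the time of consent to last visit".

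**The concern.** The planned MAAE output is one figure per group, covering everything from entry to about 13 months of age. In Group 1 that one figure has to serve objectives 1, 4, 5 and 6; in Group 2 it has to serve objectives 2, 3, 5 and 6. It mixes the primary doses, the booster visit and the roughly seven months between the end of the visit 3 window and the booster, when no study vaccine is given.

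The design makes this matter more. Both groups receive three doses of 4CMenB and two of PCV13, and their vaccines differ only at visits 2 and 3. A whole-study total adds over the very visits at which the groups can be told apart. An excess of medical attendances after one vaccine at one age could go unseen among ordinary infant illness.

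For SAEs and AESIs the issue is milder: the plan does not say whether the summary will show when the event occurred in relation to a dose. Neither AESI (febrile seizures, arthritis) is a diary term, so the by-visit solicited table does not cover them.

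**Working it through.** The SAP gives no safety event rate or safety figure to reproduce, and the sample size in section 3 does not bear on this point. The check sets outcomes against planned outputs, then works out how far pooling dilutes a post-dose excess.

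**1. Outcomes (5.3) against outputs (8.4)**

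| Class | Timing in the outcome | Timing in the planned output |
|---|---|---|
| Solicited AEs | Onset, 7 days after each vaccination | By visit and group |
| MAAEs | Onset, whole study | Group only, whole study |
| SAEs, AESIs | Onset and relationship, whole study | Group only; period not stated |

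Unsolicited AEs within 28 days of vaccination are also an outcome, but 8.4 names no table for them, so that route does not fill the gap.

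**2. Share of follow-up inside the post-dose windows**

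Inputs: follow-up from 2 to about 13 months (section 2); vaccinations at visits 1, 2, 3 and 5 (section 2.1); windows of 7 and 28 days (section 5.3). Visits 2 and 3 fall at least 28 days after the previous visit, so the windows are taken as not overlapping.

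- Follow-up: 11 × 30.4375 = 334.8 days, about 335.
- One 28-day window: 28 / 334.8 = 8.4%.
- Four 28-day windows: 112 / 334.8 = 33.5%, leaving 66.5% outside.
- One 7-day window: 7 / 334.8 = 2.1%.
- Four 7-day windows: 28 / 334.8 = 8.4%, leaving 91.6% outside.

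**3. Dilution**

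Assume an even background rate and a rate ratio RR inside a window that takes up a share f of follow-up. The whole-study ratio is 1 + f × (RR − 1).

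| Assumed RR | 28 days, one dose (f = 0.084) | 28 days, all four visits (f = 0.335) | 7 days, one dose (f = 0.021) |
|---|---|---|---|
| 2 | 1.08 | 1.33 | 1.02 |
| 3 | 1.17 | 1.67 | 1.04 |
| 5 | 1.33 | 2.34 | 1.08 |

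**4. Between the groups**

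Suppose, for illustration, that each 4CMenB dose doubles the MAAE rate for 28 days and PCV13 adds nothing. Each group has three such windows, so each total is 1 + 3 × 0.0836 = 1.25 times background, and the ratio of the two totals is 1.25 / 1.25 = 1.00. In the 28 days after visit 2 the Group 1 to Group 2 ratio would be 2 / 1 = 2; after visit 3 it would be 1 / 2 = 0.5. The whole-study totals show no difference between groups, while the by-visit table shows both contrasts.

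**The case against.** The strongest defence is that 8.4 follows the SAP's own outcome definition: 5.3 sets MAAEs over the whole study, and 8.4 reports them over the whole study. That stands, so this is an incomplete mapping to the objectives and not a contradiction. But the same outcome includes time of onset, which 8.4 does not use. A whole-study collection period does not require a report without timing.

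A reader might infer that SAEs and AESIs, too, will appear only as whole-study totals. The text does not support this. The period is stated for MAAEs alone, and a summary of SAEs and AESIs could show onset and relationship, since both are outcomes. What remains is that nothing commits the analyst to show them.

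A reader might also infer that the six safety objectives go unanswered. They do not. Solicited AEs are reported by visit, and in section 2.1 each visit corresponds to a vaccine and an age, so every objective gets a description of reactogenicity. Objectives 1 and 2 also each take both priming doses of a group together, so reporting by group partly suits them. It does not suit them fully, because the total also takes in PCV13, the booster visit and the months without vaccination.

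The dilution figures rest on assumed rates, and no between-group safety test is planned. Both points are fair: the figures illustrate the loss and do not predict it. They matter mainly for MAAEs. In about 220 infants, SAEs and AESIs are better read case by case.

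**Conclusion.** The point holds within limits. MAAEs are explicitly pooled to one whole-study figure per schedule, and no breakdown by dose or time since vaccination is specified for SAEs and AESIs, although the objectives are tied to vaccine and age and onset is already an outcome.

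About two thirds of the time behind the MAAE figure lies outside any 28-day post-dose window. With an even background rate, a doubling within 28 days of one dose would raise the total by about 8%. The share of time rests on 11 months of follow-up and four vaccination visits; the 8% also rests on the assumed even rate and the assumed doubling.

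No breakdown by timing can separate objective 5 from objective 6, because both boosters are given at the same 12-month visit. It can separate the primary doses from the booster visit, and visit 2 from visit 3. This is an inexpensive improvement to a descriptive analysis. It changes neither the sample size nor the immunogenicity analysis.

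**What to change.** Replace the MAAE sentence in section 8.4, and extend the SAE and AESI sentence, along these lines:

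> MAAEs will be tabulated by schedule group and most recent vaccination visit (V1, V2, V3, V5), split into onset within 28 days of that visit and later onset. Events before the first vaccination will be shown separately. Whole-study frequency and disease category per group will be kept. Each SAE and AESI will be listed with the preceding vaccination visit, days since vaccination and relationship to vaccination, in addition to the proportion per group.

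The 28-day split is the SAP's own window for unsolicited AEs, so no new definition is needed. State the number of infants vaccinated at each visit as the denominator.

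The cost is one table layout and one listing. Onset is already an outcome, so no new outcome data are called for. The downside is small counts: 4 visits × 2 intervals × 2 groups = 16 cells, plus the pre-vaccination row. With visits in window, the later interval after visits 1 and 2 covers at most about 14 days, and after visit 5 at most about 21 days, so those cells will be sparse. That is acceptable in a descriptive table. Fixing the layout before the data reach the statistician also avoids choosing windows after events have been seen in an open-label trial.

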### 5. Outcome Measures

### 5.1. Primary end points

Objective	Outcome Measures
To compare the immunological responses of UK infants between two different primary	1. Antibody titres against relevant 4CMenB antigens (fHbp, NadA and PorA) measured by serum bactericidal assay using human complement (hSBA) 4 weeks after 2nd dose of 4CMenB (blood sample 1 at 4 months of age for Group 1 versus 5 months of age for Group 2).
immunisation schedules of 4CMenB (2 and 3 versus 2 and 4 months of age).	
 
Antibody titres ≥ 1:4 against relevant 4CMenB antigens (fHbp, NadA and PorA) measured by hSBA assessed at 4 weeks after 2nd dose of 4CMenB (blood sample 1 at 4 months of age for Group 1 versus 5 months of age for Group 2).
 

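### As the SAP shows it, adverse events in the month after the 4-month vaccines are asked about 7 to 9 months later in Group 1 but 28 to 42 days later in Group 2, and section 8.4 makes no allowance for this

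*SAP*

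**What the plan says.** Section 2 gives two routes for non-serious events. Solicited events come from a diary: "After each vaccination visit, parents/caregivers complete a 7 day paper diary for collection of solicited AEs". For the rest, "All other unsolicited AEs are collected at each visit by study staff". No other route is given for unsolicited events, and none at all for medically attended adverse events (MAAEs).

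Table 1 places visit 4 at 5 months, 28 days after visit 3 with a window of +14 days. Group 2 has blood sample 1 there and the Group 1 cell is empty. Section 5.1 explains the blank by placing "blood sample 1 at 4 months of age for Group 1 versus 5 months of age for Group 2". Group 1's next entry after visit 3 is visit 5, at 12 months. The table is introduced as simplified and sends the reader to the protocol for full procedures.

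Section 5.3 makes two outcomes relevant here: unsolicited events in the 28 days following each vaccination, and MAAEs over the whole study. Safety objective 4 in section 4.3 concerns PCV13 given at 4 months in Group 1. Section 8.4 then plans that "MAAEs frequency and disease category will be reported by vaccine schedule group across the whole duration of the study". It says nothing about denominators or differences in ascertainment, and lists no table of unsolicited events.

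**The concern.** If events are elicited at visits, the time from a vaccination to the next visit determines how well the events after it are captured. After visits 1, 2 and 5, Table 1 shows a next visit nominally 28 days later in both groups. Visit 3 is the exception: Group 2 is seen again 28 days later, while Group 1 has no entry until 12 months. The difference follows from the randomised schedule, so randomisation does not balance it.

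Two outputs are exposed. One is the whole-study MAAE frequency by group in section 8.4. The other is the 28-day unsolicited-event outcome of section 5.3 after the 4-month vaccines, on which safety objective 4 depends. Its counterpart, objective 3 (PCV13 at 3 months in Group 2), has its enquiry at visit 3, about a month after vaccination. If recall is incomplete, fewer events would be recorded in Group 1 for reasons unrelated to the vaccines.

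**Working it through.** The SAP gives no figure for event ascertainment, so there is none to reproduce. The timing follows from its windows. The effect sizes rest on assumptions, named below.

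**Timing.** Inputs: entry at 56 to 70 days (section 2); visits 2 and 3 each 28 days after the previous visit, +14 days; visit 4 at 28 days after visit 3, +14 days; visit 5 at 12 months, +21 days (Table 1). Twelve months is taken as 365 days.

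- Age at visit 3: earliest 56 + 28 + 28 = 112 days; latest 70 + 42 + 42 = 154 days.
- Age at visit 5: 365 to 386 days.
- Group 1, visit 3 to next entry: 365 − 154 = 211 to 386 − 112 = 274 days, or 6.9 to 9.0 months at 30.44 days per month.
- Group 2, visit 3 to visit 4: 28 to 42 days.

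Group 2 then has its own gap of about 7 months, from 5 to 12 months. Only the month after visit 3 is ascertained differently.

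**28-day window after the 4-month vaccines.** Let r be the share of events still reported after the long recall and d the share of Group 1 infants lost between visits 3 and 5. Both are assumptions; d = 10% borrows the overall drop-out figure in section 3. The captured share is (1 − d) × r in Group 1, against 1 in Group 2 if nobody there is lost before visit 4.

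| | r = 1 | r = 0.8 | r = 0.5 |
|---|---|---|---|
| d = 0 | 1.00 | 0.80 | 0.50 |
| d = 10% | 0.90 | 0.72 | 0.45 |

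**Whole-study MAAEs.** Assume MAAEs are also collected at visits, the true event rate is constant and equal in both groups, capture is full over a one-month recall, and capture is r over 7 to 8 months. Over the 11 months from visit 1 to visit 6, completers contribute 3 + 8r in Group 1 and 4 + 7r in Group 2. Infants lost between visits 3 and 5 contribute 2 in Group 1 and 3 in Group 2, with Group 2 losses all placed after visit 4.

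Ratio of Group 1 to Group 2 = [(1 − d)(3 + 8r) + 2d] / [(1 − d)(4 + 7r) + 3d]

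- d = 10%, r = 1: 10.10 / 10.20 = 0.99
- d = 10%, r = 0.8: 8.66 / 8.94 = 0.97
- d = 10%, r = 0.5: 6.50 / 7.05 = 0.92
- d = 10%, r = 0.3: 5.06 / 5.79 = 0.87
- d = 0, r = 0.8: 9.4 / 9.6 = 0.98
- d = 0, r = 0.5: 7.0 / 7.5 = 0.93

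**Milder alternative.** Apply recall loss u = 1 − r only to the interval that differs and ignore drop-out. Nominal follow-up is (365 + 28) − 60 = 333 days, taking entry at about 60 days. The differing share is 28/333 = 0.084, or 42/333 = 0.126. The ratio is 1 − share × u. For u = 0.10, 0.25 and 0.50 this gives 0.99, 0.98 and 0.96 at 28 days, and 0.99, 0.97 and 0.94 at 42 days.

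Under moderate assumptions (r from 0.5 upward, d up to 10%), the two calculations span about 0.92 to 0.99. With r = 1 and d = 0 there is no effect.

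**The case against.** The strongest objection is that Table 1 is simplified and lists only vaccines and blood samples. No cell in either group mentions event collection, so an empty Group 1 cell shows no vaccine and no blood draw, not that nobody asks about events. Contact schedules are commonly left to the protocol, which was not available for this review. This stands, so the point is conditional.

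A reader might go further and infer that the safety comparison is biased in favour of the 2, 3-month schedule. The SAP does not support that as a statement of fact:

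- Collection at visits is stated for unsolicited events; for MAAEs it is inferred from the absence of another route.
- Section 8.4 states no MAAE denominator, so it cannot be said to count every infant as fully observed.
- Section 8.4 plans no by-group table of unsolicited events, so the large figures for the 28-day window concern an outcome in section 5.3, not a planned comparison.
- All six safety objectives are descriptive, with no between-group test. Objectives 3 and 4 are separate descriptions.
- Solicited events in the first week come from the diary in both groups.

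The assumed inputs also lean one way. No recall value is in the SAP, one r is used for minor and medically attended events alike, all the drop-out is placed between visits 3 and 5, and no Group 2 infant is lost before visit 4. Some Group 2 losses before visit 4 would narrow the difference.

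What remains is that, on the text as written, the interval to enquiry after visit 3 differs by group and section 8.4 does not deal with it.

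**Conclusion.** The point holds conditionally, as a cheap improvement. If the protocol provides no Group 1 safety contact at 5 months, events in the month after the 4-month vaccines are asked about some 7 to 9 months later in Group 1, against 28 to 42 days in Group 2, and never for Group 1 infants lost in between. Group 1 events are then probably under-recorded.

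For the whole-study MAAE frequency by group the effect is modest, because both groups share the long gap from 5 to 12 months: a ratio of about 0.92 to 0.99, falling to 0.87 only if recall is as low as 0.3 with 10% lost. For the 28-day unsolicited-event outcome serving objective 4 it could be substantial, with a captured share of 0.45 if half the events are recalled and 10% of infants are lost. These sizes depend on assumed recall and loss; only the timing comes from the SAP. The immunogenicity analyses are not affected.

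**What to change.** First establish whether Group 1 has a safety contact 28 days after visit 3. If it does, show it in Table 1 and use its date to close the 28-day window; the intervals to enquiry are then alike.

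If it does not, amend section 8.4 as follows:

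1. Report MAAEs, and the unsolicited events that section 5.3 makes an outcome, by the intervals visit 1 to 2, 2 to 3, 3 to 5 and 5 to 6, by group, alongside the whole-study total.
2. Count an infant in a post-vaccination denominator only if an event-collecting contact followed that vaccination.
3. For visits 3 to 5, give the time from vaccination to enquiry in each group.
4. State that the visit 3 to 5 and whole-study figures differ in ascertainment between the groups. The groups can still be shown side by side with that caution.

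The cost is some SAP wording and a few extra table columns, with fewer events in each.
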